The *primary objective* of our study is to determine the effectiveness of serial infusions of intravenous (IV) ketamine in adults *with treatment resistant depression (TRD) - diagnosed with either Major Depressive Disorder or Bipolar Disorder* - at a slower infusion time than reported in previous studies. We expect that this approach alongside with the presence of a psychiatrist with Advanced Cardiac Life Support (ACLS) training will eliminate the need for continuing anesthetic monitoring during infusion, thus leading to a more cost-effective intervention. As part of this objective, we plan to recruit 30 individuals with Treatment Resistant Depression and conduct an open label, naturalistic study using slow infusions of ketamine over a time period of 40 minutes. **The duration of this study will be 12 weeks and will include twice weekly infusions over a period of 4 weeks and weekly infusions for the following 4 weeks of the study treatment period (8 weeks). There will also be a 4 week observational period post- treatment.**

Our *hypotheses* are that patients suffering from TRD receiving weekly slow IV infusions of ketamine (0.5 mg/kg) over 40 minutes will:

1. Report similar efficacy and better tolerability than those reported with conventional schemes of 3 infusions per week over a 12 day period.
2. Report less psychiatric side effects measured by changes in test scores on the Montgomery-Åsberg Depression Rating Scale (MADRS), Quick Inventory of Depressive Symptomatology (QIDS) and Young Mania Rating Scale (YMRS) compared to those previously reported with conventional schemes of serial ketamine infusions.
3. Report an almost immediate effect based on the PANSS and Q-LES-Q scales which will be administered after the 40 min infusion period.
4. Report less suicidal ideation measured by changes in scores on the Scale for Suicide Ideations (SSI; Beck et al., 1979), and the Suicide Status Form (SSF; Conrad et al., 2009) scores compared to that previously reported with conventional schemes of serial ketamine infusions.
5. Report a better global outcome of treatment measured by a decrease in scores on in the Clinical Global Impression Scale (CGI; Guy, 1976) score compared to that previously reported with conventional schemes of serial ketamine infusions.
6. Experience less hemodynamic changes in blood pressure and heart rate compared to than those previously reported with conventional schemes of serial ketamine infusions.

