Thus, in the current study we want to naturalistically explore the antidepressant effects of serial slow IV infusions (40 minutes) of ketamine at a dose of 0.5 mg/kg, over a treatment period of 8 weeks in an academic psychiatric hospital. This is a minimal sedation treatment. This dosage is the highest used so far in the literature and was selected because of its reported benefits in a psychiatric population. The dosage will be calculated using the patient's weight in kilograms. For dosing purposes, 0.5-0.9 round up to the next dose and from .01-0.49, we will round down to the lower dose. The primary outcome measure of this study will be *remission* estimated based on the severity of depressive scores (MADRS). After the 8 weeks of treatment, there will be a four week observational period. During the observational period, participants will receive treatment as usual and will be contacted over the phone for follow-up questions regarding their overall health status, mood and clinical state using MADRS, YMRS and CGI. They will also complete a neurocognitive task at the end of the 4 week observational period.

B. Innovation

The approach taken in the current study is novel for two reasons: 1) we are testing a novel dosage and time of infusion for the administration of slow infusion, repeated IV ketamine targeting TRD; 2) this is the first naturalistic study of repeated ketamine IV infusion for MDD and BD in a psychiatric setting. Furthermore, this will constitute the largest study conducted to date testing the antidepressant effects of repeated ketamine infusions in a combined population of MDD and BD patients with TRD.

C. Approach

The current project will exploit the feasibility of recruitment associated with ongoing studies at the University of Texas, Center of Excellence on Mood Disorder, Department of Psychiatry and Behavioral Science in Houston aimed at identifying the neural correlates of BD. The clinical sample will include individuals from various ethnic/racial backgrounds, reflecting the local community in the greater Houston area. We will use slow infusions of ketamine over a time

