The BAC-A is based on the Brief Assessment of Cognition in Schizophrenia (BAC-S). The BAC-S has been validated both linguistically and psychometrically in a number of psychiatric populations, including patients with schizophrenia and BD (Cuesta et al., 2011; Hill et al., 2013; Kuswanto, Sum, & Sim, 2013; Salgado et al., 2007; Segarra et al., 2011). It has been shown to be as valid and sensitive as a traditional neuropsychological assessment and takes approximately 35 minutes to administer (Keefe et al., 2004; Velligan et al., 2004). Six of the 8 subtests of the BAC-A match those found in the BAC-S. These tests are the Token Motor Task, Symbol Coding, List Learning, Digit Sequencing Task, Category Instances (Animals) and

Controlled Oral Word Association Test (F and S-words), Tower of London (Keefe et al., 2004). In addition to these 6 subtests the BAC-A comprises the Emotion Inhibition Test (a modified version of the Emotional Stroop task (LaMonica, Keefe, Harvey, Gold, & Goldberg, 2010; Williams, Mathews, & MacLeod, 1996)) and the affective auditory verbal learning test (Affective interference test). The latter task is similar to the Affective Auditory Verbal Learning Test (AAVLT) (Snyder & Harrison, 1997). Assessments will be conducted prior to the treatment period, 4, and 8 weeks into the treatment. To avoid potential learning bias we will use parallel versions of the word lists for the Emotion Inhibition Test, Tower of London, and the Verbal Memory Tests to assess cognitive changes over the course of the ketamine treatment.

Study design

We will follow an AB design and clinical/cognitive assessments will be taken at baseline, week 4, week 8, and week 12. Given the preliminary nature of this treatment study this open label trial aims to generate an effect size for a subsequent RCT and/or future grant application. No *a priori* estimates of the power/effect size were therefore calculated.

Timeline	After Each Infusion	Baseline	Week 4	Week 8	Weekly Follow-up Phone Calls	Week 12
SCID-I		X				
Clinical scales (MADRS, CGI, YMRS)		X	X	X	X	X
PANAS, Q-LES-Q, self-report	X					
BAC-A		X	X	X		X
Blood tests/Sample		X	X	X		X
Urine drug test	X	X				

Study sample

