We will recruit adult patients aged 18-65 years with MDD or BD, with documented TRD (according to DSM-IV TR), and who have failed (defined as patient does not reach remission within the 8 week trial of an antidepressant or combination at a therapeutic dose) of at least two trials of first line evidence-based treatments and/or ECT.

Exclusion criteria

- 1) Being younger than 18 of age or older than 65.
- 2) Diagnosed with intellectual disability, e.g. mental retardation (MR), neurodegenerative diseases, e.g. early-onset neurocognitive disturbances such as frontotemporal dementia (FTD) or behavioral disorders, e.g. adult onset Attention Deficit Hyperactivity Disorder (ADHD).
- 3) Diagnosed with BD-NOS or rapid cycling BD
- 4) Diagnosed with personality disorders (PD).
- 5) Previously or currently diagnosed with psychosis (schizoaffective disorder - SAD) or schizophrenia - SCZ).
- 6) Current major medical problems that affect brain anatomy, neurochemistry, or function, e.g., obstructive sleep apnea requiring Continuous Positive Airway Pressure (CPAP), liver insufficiency, kidney insufficiency, cardiovascular problems, systemic infections, cancer, auto-immune diseases, and any brain disorder (seizure disorder, stroke, dementia, degenerative neurologic diseases); history of any brain diseases, including seizures, stroke, meningitis, encephalitis, dementia, degenerative brain diseases, and head injury with loss of consciousness for any period of time.
- 7) Diagnosed specifically with a cardiovascular disorders such as Arrhythmias, Chronic Heart Failure, Myocardial Infarction (MI) or suffering from Chronic Obstructive Pulmonary Disease (COPD) or asthma. Suffering from uncontrolled hypertension or diastolic BP over 100. Cardiac clearance prior to enrolling in the study/medical records from physician will be required *per patient's PCP*. (Diastolic BP must be less than 100 Systolic BP less than 165 and greater than 85 Heart rate less than 100.)
- 8) Patients with thyroid condition and are not currently euthyroid or on stable treatment regimen.
- 9)
- 10) Patients with increased risk of laryngospasm, active upper respiratory infections, respiratory depression, increased intracranial pressure, hyperthyroidism, or porphyria.

- 11) Current substance abuse or dependence. Only patients who achieved stable, full remission for at least 6 months will be included.

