- 12) Pregnancy or Breast feeding. All female in reproductive age will undergo pregnancy tests. Female participants will be required to provide evidence of use of contraceptives during the course of the study.
- 13) Unable to understand the design and requirements of the study
- 14) Unable to sign the informed consent for any reason
- 15) An assigned responsible adult has provided assent to assist in patient's study participation. The responsible adult agrees to be present at each study appointment as well as provide transportation to study appointments for the patient.

Non responders

If a patient does not respond to the study treatment by their 4th treatment they will be removed from the study due to non-response. A successful response to study treatment will be at least a 30% reduction in MADRS scores from screening until the 4th treatment. Again if a patient does not respond by the 4th treatment, they will be excluded from the study.

Unanticipated Hospitalizations

If a patient needs to be hospitalized for worsening of symptoms or for their own personal safety, they will be removed from their study participation and their study treatment will end at that time.

Feasibility

Subject recruitment: Our center has access to a large patient pool (drawing from a metropolitan area of about 5.5 million people) and well-established ability to recruit patients with mood disorders. [name] is the department chair for Psychiatry and Behavioral Sciences and Director of the University of Texas, Center of Excellence on Mood Disorders. He successfully completed a large number of studies over the past 20 years with excellent recruitment of MDD and BD subjects at this site. We will also recruit participants through doctor referrals. Participants will be exclusively outpatients.

Funding of the study: given the preliminary nature of this study we plan to use departmental funding for the current study and then possibly apply for a larger grant later on once we have collected preliminary data and calculated optimal power/effect sizes for ketamine treatment in individuals with TRD.

Data analysis

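### Remission is judged on MADRS alone in a sample that includes bipolar patients, so a patient with low MADRS but raised YMRS at week 8 counts as a remitter and no planned analysis separates such patients

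*Combined protocol and SAP*

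**What the plan says.** **Outcome.** The last paragraph of the Background and Rationale (2.0 Research Strategy, A. Significance) names remission as the primary outcome, "estimated based on the severity of depressive scores (MADRS"). It gives no MADRS cut-off, no time point and no condition on mania.

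**Population.** Study sample: "We will recruit adult patients aged 18-65 years with MDD or BD". Among bipolar patients, the exclusion based on bipolar type is "Diagnosed with BD-NOS or rapid cycling BD"; other bipolar diagnoses may enter. No planned split between the two disorders is given.

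**Schedule.** In the Study design timeline, one row, "Clinical scales (MADRS, CGI, YMRS"), is marked at baseline, weeks 4, 8 and 12, and the weekly follow-up calls. The Background and Rationale confirms that the calls cover "mood and clinical state using MADRS, YMRS and CGI".

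**Role of YMRS.** Hypothesis 2 lists it among the measures of psychiatric side effects: "Report less psychiatric side effects measured by changes in test scores on the" MADRS, QIDS and YMRS, set against earlier ketamine schemes. It has no part in the definition of remission.

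**Analysis.** The Data analysis section plans comparisons of responders with non-responders, random effects models of clinical scores, predictive values and a Kaplan-Meier analysis of time to relapse. It mentions neither YMRS nor mania.

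**Related rule.** Under Unanticipated Hospitalizations, a patient admitted for worsening or for safety leaves the study. The outcome status of that patient is not stated.

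**The concern.** MADRS measures depressive symptoms only. A patient who has moved from depression into hypomania or mania may score low on it while being unwell in the other direction. In a purely unipolar sample this would be a small matter. Here the protocol presents the trial as the largest repeated-infusion study in a combined MDD and BD population, so what remission means in a bipolar patient bears on the main result.

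Three features raise the stakes. The trial is open-label with a single arm, so no control group carries the same misclassification. Estimating response and remission rates is one of its stated purposes. Its results are also meant to supply the effect size for a later randomised trial, so an overstated remission rate would carry forward into that design.

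Splitting the results by diagnosis would not cure this, because a table for bipolar patients alone would contain the same misclassified patients.

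**Working it through.** The plan has no figure to reproduce: it calculates no power and gives no expected remission rate or switch rate. The check has two parts.

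**1. Does any rule reclassify a patient with low MADRS and raised YMRS at week 8?**

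- Definition of remission: MADRS only, so no.
- Hypothesis 2: concerns changes in scores compared with published reports. A mean YMRS change over 30 patients can hide one or two large individual rises, and it does not alter who is a remitter. No.
- Global impression scale, including the bipolar version named under Clinical assessment: not linked to remission. No.
- Hospitalization rule: does not cover a switch without admission and assigns no outcome. No.
- Data analysis: no step uses YMRS. No.

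The patient is therefore counted as a remitter. The documents do not say so in words; it follows from the definition and the absence of any other rule.

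**2. How large could the effect be?**

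Inputs: 30 patients planned (from the protocol); bipolar patients B = 10, 15 or 20 (assumed); proportion switched at the rated visit s = 5%, 10% or 20% (assumed).

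Weight of one patient: 1/30 = 3.3 points.

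Expected switches = B × s. Ceiling on average inflation = 100 × B × s / 30, reached only if every switched patient also meets the MADRS criterion. Chance of at least one switch = 1 − (1 − s)^B.

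| B | s | Expected switches | Ceiling (points) | Chance of ≥1 switch |
|---|---|---|---|---|
| 10 | 5% | 0.5 | 1.7 | 0.40 |
| 10 | 10% | 1.0 | 3.3 | 0.65 |
| 10 | 20% | 2.0 | 6.7 | 0.89 |
| 15 | 5% | 0.75 | 2.5 | 0.54 |
| 15 | 10% | 1.5 | 5.0 | 0.79 |
| 15 | 20% | 3.0 | 10.0 | 0.96 |
| 20 | 5% | 1.0 | 3.3 | 0.64 |
| 20 | 10% | 2.0 | 6.7 | 0.88 |
| 20 | 20% | 4.0 | 13.3 | 0.99 |

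If only a fraction f of switched patients meet the MADRS criterion, the ceiling is multiplied by f. With B = 15, s = 10% and f = 0.5 (also assumed): 15 × 0.10 × 0.5 = 0.75 patients, 0.75/30 = 2.5 points, and a chance of at least one misclassified patient of 1 − 0.95^15 = 0.54.

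**Effect on a reported rate.** Take 15/30 as an illustration, using the 50% that the background cites for a 10-patient study of slower, lower-dose infusions. Exact 95% intervals:

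| Patients reclassified | Remission rate | 95% interval |
|---|---|---|
| 0 | 15/30 = 50.0% | 31.3% to 68.7% |
| 1 | 14/30 = 46.7% | 28.3% to 65.7% |
| 2 | 13/30 = 43.3% | 25.5% to 62.6% |
| 3 | 12/30 = 40.0% | 22.7% to 59.4% |

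These shifts are smaller than the sampling error (half-width (68.7 − 31.3)/2 = 18.7 points), but they always go the same way.

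**The case against.** The strongest reply is that efficacy and harm are kept apart on purpose. The study asks about antidepressant effect, and MADRS measures that. YMRS has its own hypothesis, a place in the schedule and repeated ratings in follow-up. Hypothesis 1 compares efficacy with earlier schemes, and the background describes an earlier repeated-infusion study whose response criterion was a MADRS reduction. A composite primary outcome would weaken that comparison, and making a switch a relapse event changes what the Kaplan-Meier curve estimates. This stands, and it is why the MADRS-only rate should stay.

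The evidence on size is also thin. The assumed switch rates have no source in the documents. The one related finding, in the 10-patient study cited above, was no significant rise in YMRS, though at a different dose and infusion time. Two bipolar groups are excluded. This stands too, and the figures above are ceilings.

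Several stronger readings are tempting, but the documents do not support them:

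- *The response rule needs a YMRS condition as well.* The Non responders section says: "A successful response to study treatment will be at least a 30% reduction in MADRS scores from screening until the 4th treatment". That rule decides who is removed from the study, so adding a condition would change a rule on stopping treatment. At two infusions a week, the 4th treatment also falls at about week 2, where the timeline schedules neither scale.
- *A switched patient is certain to enter time to relapse as a responder.* The Data analysis section refers to response at end point without defining it, and nothing says that the removal rule is that definition.
- *The plan reports mania as benefit.* It monitors YMRS separately; what it lacks is the link between the two scales at patient level.
- *Half the sample is bipolar, or there is a 79% chance of a misclassified remitter.* No split is given, and 0.79 is the chance of at least one switch under assumed inputs.

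The missing MADRS cut-off and time point for remission are a separate and larger gap.

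**Conclusion.** The point holds for remission. Under the plan's definition, a patient with low MADRS and raised YMRS at a scheduled visit is a remitter, and no planned analysis would reveal it. Week 8 is taken here as the rating that matters because it ends treatment; the plan does not say so.

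With a denominator of 30, each such patient is worth 3.3 points. For 10 to 20 bipolar patients and 5% to 20% switching, the average inflation is at most 1.7 to 13.3 points. Both ranges are assumptions, and the ceiling is reached only if every switched patient meets the MADRS criterion. If fewer than 30 patients are analysed, each one weighs more.

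This limits what the trial can call remission in a mixed sample, and the effect size that it hands on. It does not make the MADRS-only rate invalid as a measure of depressive symptoms.

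**What to change.** In the outcome paragraph of the Background and Rationale and in Data analysis, for analysis only:

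1. Keep the MADRS-only remission rate.
2. Beside it, prespecify the number of MADRS remitters whose YMRS at the same scheduled visit is at or above a cut-off that the sponsor fixes before analysis. Report this as affective switch, overall and among bipolar patients.
3. Prespecify the remission rate with those patients counted as non-remitters.
4. Apply the same cross-classification to responder status wherever both scales are rated: weeks 4, 8 and 12 and the follow-up calls.
5. Show time to relapse with switch counted as an event, as a sensitivity analysis.

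Leave the 4th-treatment removal rule unchanged. It depends on a MADRS comparison, "at least a 30% reduction in MADRS scores from screening until the 4th treatment", while the timeline lists no MADRS rating at that treatment; the sponsor should reconcile those two places.

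The cost is a few sentences, a little more analysis, and a second remission figure that may be slightly lower. No new data are needed, since both scales are already collected at the visits used.

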Routine blood tests will be performed in fasted state before the first ketamine infusion, prior to infusions at week 4 and at week 8. These tests aim to test the participants' overall health state. Blood samples will also be used for genetic testing and to measure levels of inflammatory markers. Samples will be stored at [REDACTED]. As stated in the consent form, participants will not receive any medical results or genetic counseling by providing a sample. All participants will undergo urine drug tests before each ketamine infusion.

Clinical questionnaires (e.g. MADRS) will be administered at baseline, at weeks 4, 8, and Week 12. The PANSS and Q-LES-Q scale will be administered after each ketamine infusion is completed. During the course of infusions, patients will receive treatment-as-usual from their primary psychiatrists as would be the case in a traditional therapeutic setting. There will be no changes in medication regimen throughout the 8 week treatment period as well as the 4 week observational follow-up period. Participants will be provided with a contact card directing them to the nearest ER/physician in case of emergency. Participants will be contacted weekly during the 4 week observational period to review the patient's health status and administer clinical scales. Upon conclusion of the intervention patients will be offered the opportunity to come back for maintenance sessions. The frequency of these sessions will depend on the patient's wishes and the physician's clinical judgment. The maximum session frequency will be once every month for a maximum of 12 months.

Assessment

The protocol consists of two components: clinical and cognitive assessments.

Clinical assessment

This evaluation will obtain family history and demographic data. Copies of any recent medical evaluations (past medical history, physical exam, etc.) will be requested from treating clinicians and health care providers. We will perform a urine drug screening (UDS) to rule out recent undisclosed use illicit substances. Demographic information is obtained through a standardized form and covers: age, race, gender, education (information both on siblings and their parents), religion, and socioeconomic status. Participants will fill out mood questionnaires rating the severity of the clinical symptoms.

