-MINI Interview: This is the standard psychiatric research evaluation for ascertainment of psychiatric diagnosis in the context of research studies (Sheeha et al., 2016)). It is a comprehensive structured interview for determining axis I diagnosis according to the DSM-V.

-Clinical Global Impression Scale (CGI): This is a clinical instrument to assess global changes in patients' status in clinical studies. We will use the CGI-BD, for use with BD patients (Guy et al., 1976).

-Montgomery-Åsberg Depression Rating Scale (MADRS): this scale rates depressive symptoms, and its psychometric properties are well-established (Montgomery et al. 1979).

-Young Mania Rating Scale (YMRS): This is a well-established clinical severity rating scale for manic symptoms that has adequate inter-rater reliability and internal consistency (Young et al., 1978).

- Quality of Life Enjoyment and Satisfaction Questionnaire (Q-LES-Q): this scale is patient-reported and measures the degree of enjoyment and satisfaction experienced by subjects in various areas of daily functioning (Endicott et al., 1993).

-

- The Positive and Negative Syndrome Scale (PANSS) includes 30- items and was conceived as an operationalized, drug-sensitive instrument that provides balanced representation of positive and negative symptoms. It is composed of four scales measuring positive and negative syndromes, their differential, and general severity of illness. The Positive and Negative Syndrome Scale (PANSS) for Schizophrenia. Kay, Stanley R.; Fiszbein, Abraham; Opfer, Lewis
A. Schizophrenia Bulletin, Vol 13(2), 1987, 261-276. This scale will be administered following each ketamine infusion to assess acute changes in mood.

Self-report questionnaires to assess mood and anxiety:

1. Adult (Brief Dissociative Experiences Scale [DES-B]—Modified): Frequency: After every injection, to monitor the dissociative side effects, Scale features: simple, easy to use, new DSM-5 self-rated scale
2. Severity Measure for Generalized Anxiety Disorder—Adult : Every 4 weeks, to measure the severity of anxiety. Scale features: simple, easy to use, new DSM-5 self-rated scale
3. Snaith–Hamilton Pleasure Scale: every 4 weeks, to measure the level of anhedonia, Scale features: easy to use, used before in ketamine studies, self-rated scale

Cognitive assessment

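### The schedule lists the self-report scales only after infusions: dissociation has no pre-treatment score, and anxiety and anhedonia timing conflicts with the text

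*Combined protocol and SAP*

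**What the plan says.** All references are to the combined protocol and SAP, section 2.0 Research Strategy, unless stated otherwise.

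- **Timeline table (Study design).** The row "PANAS, Q-LES-Q, self-report" carries one mark, in the after-infusion column. The clinical scales (MADRS, CGI, YMRS) have a separate row, marked at baseline, weeks 4, 8 and 12, and the follow-up calls.
- **Clinical assessment.** Under "Self-report questionnaires to assess mood and anxiety" three scales are listed. The brief dissociation scale (DES-B) is given "After every injection, to monitor the dissociative side effects". The generalized anxiety severity measure is given "Every 4 weeks, to measure the severity of anxiety". The Snaith–Hamilton scale is given "every 4 weeks, to measure the level of anhedonia".
- **General grid.** Study design says that "clinical/cognitive assessments will be taken at baseline, week 4, week 8, and week 12", and the Approach section says "Clinical questionnaires (e.g. MADRS) will be administered at baseline, at weeks 4, 8, and Week 12". Neither sentence names any of the three self-report scales.
- **Design.** The trial is open-label with one arm, described as an AB design, and is meant to supply an effect size for a later randomised trial.

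**The concern.** With no control arm, a patient's own pre-treatment score is the only comparator inside the trial. If the self-report forms are completed only after infusions, that score does not exist.

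The first post-infusion form cannot stand in for it. Hypothesis 3 expects an almost immediate effect after the infusion, on other scales. The Potential Risks section cites 58.3% of patients in an earlier study feeling strange or unreal in the four hours after an infusion. A first post-infusion dissociation score may therefore already contain the effect that it is meant to detect, mixed with whatever dissociation the patient had at entry. The exclusion criteria name no dissociative disorder, so prior dissociation is not ruled out.

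For anxiety and anhedonia there is also a practical problem: a site cannot follow both the table and the text. A baseline that is not collected before the first infusion cannot be recovered.

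**Working it through.** No sample size, power or error rate is involved, and Study design states that none was calculated. The check sets the places side by side, counts forms, and asks which contrasts the data would support.

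**Step 1: number of infusions.** The objectives give two a week for 4 weeks and one a week for 4 weeks: 2 × 4 + 1 × 4 = 12. The Reimbursement section also gives 12.

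**Step 2: forms per patient completing treatment**, reading the table's self-report label as covering all three scales.

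| Scale | Table | Text | Agree? | Stated pre-treatment score |
|---|---|---|---|---|
| DES-B | up to 12, after infusions | up to 12, after infusions | Yes | None in either place |
| Anxiety | up to 12, after infusions | 3 (weeks 4, 8, 12), or 4 with baseline | No | None in table; in text only if the general grid applies |
| Anhedonia | up to 12, after infusions | 3, or 4 with baseline | No | Same as anxiety |

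The timing conflict covers 2 of 3 scales. The table gives a pre-treatment score for 0 of 3.

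**Step 3: what can be estimated.** Let b_k be the patient's background level just before infusion k, and d_k the effect of that infusion when the form is completed. Ignoring measurement error, the post-infusion score is y_k = b_k + d_k.

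- Available: y_12 − y_1 = (b_12 − b_1) + (d_12 − d_1), the change across post-infusion scores.
- Not available without a pre-treatment score: y_1 − b_1 = d_1, the rise at the first infusion.
- With one baseline score B = b_1: y_1 − B = d_1, but y_k − B = d_k + (b_k − b_1). Pre-existing dissociation at entry is removed; a later shift in background is not.

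**Step 4: early removal.** Under Non responders, patients without a 30% MADRS reduction by the 4th treatment leave the study. At two infusions a week that is 4 / 2 = 2 weeks. If the four-weekly forms begin at week 4, these patients supply no anxiety or anhedonia score at all. The comparison of baseline characteristics between responders and non-responders planned under Data analysis could not then include these scales. A first-to-last contrast over all 12 infusions is likewise limited to patients retained because they responded.

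**The case against.** **The general grid may already supply a baseline.** The three scales sit under Clinical assessment, and Study design places clinical and cognitive assessments at baseline and weeks 4, 8 and 12. A four-weekly form fits that grid naturally and would give four assessments. This stands as a reasonable reading for anxiety and anhedonia, so a reader should not infer that the documents give those two scales no baseline anywhere. It remains an inference. The scales are not named in the grid sentences, and the table gives MADRS, CGI and YMRS their own row with a baseline mark while the self-report row has none. It does not help DES-B, whose only stated timing is after injections.

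**The row label is ambiguous.** Its self-report entry could mean DES-B alone, or could simply describe the row. The table would then omit the anxiety and anhedonia scales rather than move them, and the contrast of 12 forms with 3 or 4 would not arise for them. This also stands, but on every reading the table shows no baseline for any of the three.

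**The scales are peripheral to the stated aims.** No hypothesis names them, nor does the Data analysis section. The primary outcome is MADRS-based remission. Hypothesis 1 speaks of tolerability without naming dissociation, and hypothesis 2 measures psychiatric side effects by MADRS, QIDS and YMRS. DES-B is described as monitoring. This stands and limits the weight of the point.

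**Distortion by acute drug effects is not documented for these forms.** The plan gives neither minutes after infusion nor a recall window, so how far a post-infusion anxiety or anhedonia score would be affected is unknown. This stands.

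**Q-LES-Q matters more.** It shares the row, is likewise given only after infusions, and is named in hypothesis 3. That is a related gap, which editing the same row should also address.

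**Conclusion.** The point holds in limited form.

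- **Anxiety and anhedonia:** table and text conflict on timing, and a baseline exists only if the general grid is taken to cover them.
- **DES-B:** timing agrees in both places, but neither gives a pre-infusion score. Change from pre-treatment cannot be estimated under any reading of the schedule.

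A reader might infer that no change at all can be estimated on these scales, or that the timing conflict covers all three. The documents support neither. Up to 12 post-infusion scores allow change across infusions, and the conflict covers two scales of three. What is lost is change from pre-treatment: for DES-B outright, and for anxiety and anhedonia if the table is followed.

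The effect is on what the trial can say about dissociative side effects and about anxiety and anhedonia; the primary outcome is not touched. The change should be made because it is cheap and a missed baseline is irrecoverable. This conclusion assumes that the single mark stands in the after-infusion column, as the table shows. The Approach section, which also gives Q-LES-Q after each infusion, is consistent with that.

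**What to change.** Split the table row and reconcile it with the Clinical assessment text:

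- **DES-B:** at baseline before the first infusion, and after each infusion.
- **Anxiety and anhedonia scales:** named explicitly at baseline and weeks 4, 8 and 12, completed before any infusion that day.
- **Analysis:** report change from baseline for all three, and state that one baseline DES-B accounts for dissociation present at study entry but not for shifts in background level before later infusions.

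The cost is a table edit and one extra set of short self-rated forms at a baseline visit that already takes place. The protocol itself describes these scales as easy to use.
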